## **Scientific Background**

One of the principal mechanisms associated with the maintenance of and relapse to alcohol use is stress. Neuroimmune function is a key system linked to negative reinforcement drinking and to the development of alcohol use disorder (AUD). Stress and chronic alcohol consumption have been found to increase microglial activity, a marker of neuroinflammation. However, a provocation study to examine neuroinflammation-induced drinking has not been developed in humans and has direct clinical significance for the development and evaluation of pharmacotherapies targeting the neuroimmune system.

Endotoxin, also called lipopolysaccharide (LPS), is well-known to induce neuroinflammation and acute stress, and a growing literature indicates that neuroinflammatory processes are involved in alcohol-motivated behavior. In rodents, systemic administration of LPS resulted in prolonged increases in levels of proinflammatory cytokines, an effect potentiated by alcohol. Administration of inflammatory signaling by LPS demonstrated long-lasting increases in voluntary alcohol intake in mice, which may be due to the effects of acute stress induced by LPS – as LPS has transient effects on neuroinflammatory responses. Proinflammatory cytokines that increased in rat brain following alcohol or LPS were also increased in the brain of humans with alcohol dependence. In alcohol-dependent individuals, LPS stimulated inflammatory pathways correlated with alcohol craving and short-term alcohol withdrawal was associated with the recovery of LPS-dependent receptors. Regarding stress, LPS administration increased plasma ACTH in alcohol-exposed rats and dose-dependently increased proinflammatory cytokines, cortisol, anxiety, and depressive symptoms in humans; altogether, supporting a clear role for neuroinflammation in stress and alcohol use. To our knowledge, the effect of LPS, which directly induces neuroinflammation compared to other stress challenges, on alcohol self-administration in humans with AUD has not been studied, identifying an area of weakness in the scientific rigor of previous work. The first step in addressing this gap is to examine peripheral measures of neuroinflammation (e.g., cytokine levels) and relate that to drinking behavior in the human laboratory. By collecting subjective and objective measures of stress (e.g., mood, cortisol, ACTH), we can also determine whether LPS administration is related to stress-reactivity in individuals with AUD.

Over the past decade, rates of AUD have continued to increase more so in women (84%) than in men (35%). Women also experience exacerbated health risks associated with drinking, including brain atrophy, liver inflammation, cardiovascular disease, and neurotoxicity when compared to men. Identifying effective mechanisms underlying problem alcohol use in women vs. men remains a priority. Stress and greater neuroimmune response are associated with alcohol use for both women and men, but play an especially critical role in women. Research identifies that alcohol administration leads to higher cortical levels of proinflammatory cytokines associated with oxidative stress in female compared to male mice and higher plasma endotoxin levels in healthy women compared to men. Problematic drinking in women is also associated with higher plasma levels of proinflammatory cytokines compared to men.

Importantly, we plan to calculate effect sizes for the interaction between sex and treatment (endotoxin vs. placebo) on drinking behavior and associated mechanisms (e.g., peripheral cytokines, craving, cortisol, ACTH, sex hormones) during the 2-hour alcohol self-administration period, as these may be important mechanisms underlying drinking behavior in women vs. men.

Elucidation of neuroinflammatory mechanisms underlying drinking can inform on the involvement of neuroinflammation in alcohol use, as well as potential sex differences in mechanisms underlying how neuroinflammation influences acute drinking. This data will inform sex-appropriate mechanisms and potential treatment targets, such as neuroimmune modulators, for alcohol use in individuals with AUD, as well as inform future research on disentangling the effect of LPS vs. psychological stress (e.g., stress vs. neutral imagery) on subsequent drinking behavior.

### **Study Design and Methods**

We will examine whether endotoxin, known to induce acute stress and neuroinflammation, increases acute drinking behavior in a sex-dependent manner. We will recruit 32 individuals with AUD (50% women). Subjects will undergo a single laboratory session in which we will evaluate alcohol consumption.

Subjects will be informed to not drink 24 hours prior to the laboratory session (confirmed by breath alcohol reading and self-report). Smokers will be instructed to smoke as they usually do prior to coming to the YCCI/HRU. If participants report or test positive for breath alcohol, drug use, alcohol withdrawal, or pregnancy they will not complete the laboratory session. If participants present with alcohol withdrawal (CIWA  $\geq 8$ ), the participant will be evaluated by the study MD for possible study removal and referral to detox. An IV cannulae will be inserted in the non-dominant arm to obtain blood samples throughout the session. LPS (0.4ng/kg; *Escherichia coli*) or placebo (saline) injections will be performed through the IV cannulae, approximately 1 hour and 45 minutes before the alcohol self-administration period. This dose has been safely administered to healthy humans previously (range 0.2 – 1.0ng/kg i.v. in healthy human subjects).

Ad-libitum drinking will occur over a 2-hour period. A video camera will be present in the room during this session to monitor drinking behavior. Subjects will be provided a pre-determined amount of their preferred beverage designed to raise BALs to 0.12 g/dL. Participants will be provided with their preferred beverage (e.g., beer, wine, liquor, mixed drink) as a bolus at the start of the session. The bolus dose is provided in a plastic pitcher (e.g., beer) or a plastic carafe (e.g., wine, mixed drink) depending on the participant's preferred beverage. The participant is also provided with a drinking vessel (e.g., plastic pint glass, plastic wine glass, plastic tumbler). The participant can pour as much or as little of their preferred beverage as they like from the pitcher or carafe into their drinking vessel, and choose to drink as much or as little as they like throughout the 2-hour alcohol self-administration session.

Prior to discharge, serum endotoxin will be drawn. Subjects will remain in the YCCI/HRU overnight, at which time their breath alcohol levels will be below 0.02% (confirmed by two BAC readings). Participants who are deemed to be belligerent by study/HRU staff will be

immediately discontinued at the discretion of the PI. Participants will be asked to remain in their room until reaching a safe BAC at which time they will be dismissed. If they continue to behave in a threatening manor, hospital security will be called to supervise the participant until they can be safely discharged from the HRU.

## **Eligibility Criteria**

After obtaining written informed consent, potential subjects will be screened for eligibility. In other words, potential subjects will sign consent prior to beginning screening procedures. We will administer the Structured Clinical Interview for DSM-5 (SCID-5) to confirm AUD and exclude other primary psychiatric and substance abuse disorders (other than tobacco use disorder). We will record alcohol use over the prior 90 days with the Timeline-Follow Back Interview (TLFB), and quantify lifetime patterns of alcohol use with the Lifetime Drinking History. The consequences of alcohol use and severity will be measured with the Short-Inventory of Problems for Alcohol Use and the Alcohol Use Disorders Test (AUDIT), respectively. The Clinical Institute Withdrawal Assessment of Alcohol Scale, Revised (CIWA-R) will assess alcohol withdrawal symptoms. Patients with CIWA-R  $\geq 8$  will not be eligible to participate. Subjects will undergo medical screening, including medical history, medication use, allergies, a physical exam, an EKG, basic blood chemistries, urine drug toxicology screen, and a blood pregnancy test for women. The study physicians will review the subject's medical status and medical eligibility criteria. Eligible subjects will be randomized to receive endotoxin or placebo. If potential participants are found to be suicidal or are experiencing any psychiatric symptoms or distress during the screening process, they will receive short-term support from the study team (including clinical psychologists and study physicians) and will be connected to a local emergency department and their physician or therapist for ongoing care.

### **Inclusion Criteria:**

- 1) Age 21-65;
- 2) Able to read and write English;
- 3) Meets DSM-5 criteria for current (past 6 months) moderate to severe alcohol use disorders;
- 4) Drinking criteria: Males - Drinks  $> 14$  drinks per week and exceeds 4 drinks per day at least twice per week; Females -Drinks  $> 7$  drinks per week and exceeds 3 drinks per day at least twice per week.
- 5) Must meet drinking criteria during a consecutive 30-day period within the 90 days prior to baseline;
- 6) Laboratory sessions will be scheduled such that subjects will not have major responsibilities on the following day which might limit drinking during the self-administration session (e.g., job interview, exam);
- 7) Negative urine pregnancy test for women.

### **Exclusion Criteria:**

- 1) Participants with any significant current medical conditions (neurological, cardiovascular [including hypertension or hypotension: sitting BP  $>160/100$  or  $<90/60$  mmHg at baseline screening], endocrine, thyroid, renal, liver), seizures, delirium or hallucinations, or other unstable medical conditions including HIV;
- 2) Current DSM-5 substance use disorders, other than alcohol or nicotine;

- 3) A positive test result at intake appointment on urine drug screens conducted for illicit drugs, excluding cannabis;
- 4) Past 30 day use of psychoactive drugs including anxiolytics and antidepressants;
- 5) Women who are pregnant or nursing, or fail to use one of the following methods of birth control unless she or partner is surgically sterile or she is postmenopausal (hormone contraceptives [oral, implant, injection, patch, or ring], contraceptive sponge, double barrier [diaphragm or condom plus spermicide], or IUD);
- 6) Suicidal, homicidal or evidence of current (past 6-month) severe mental illness such as schizophrenia, bipolar disorder or major depression, or anxiety disorders;
- 7) Subjects treatment-seeking or who are currently in treatment for alcohol use;
- 8) Subjects with medical conditions contraindicating alcohol use (e.g., liver enzymes  $\geq 3 \times$  normal);
- 9) Subjects likely to exhibit clinically significant alcohol withdrawal during the study. We will exclude subjects who a) have a history of perceptual distortions, seizures, delirium, or hallucinations upon withdrawal, or b) have a score of  $> 8$  on the Clinical Institute Withdrawal Assessment scale at intake appointments;
- 10) Participation within the past 8 weeks in other studies that involve additive blood sampling and/or interventional measures that would be considered excessive in combination with the current application.
- 11) Subjects  $> 38$  on the Alcohol Use Disorders Identification Test (AUDIT)
- 12) Subjects with resting pulse  $> 100$  at challenge
- 13) Subjects with recent (past 2 weeks) acute illness or vaccination
- 14) Subjects with  $>$ Grade 2 laboratory abnormalities on screening

## **Statistical Considerations**

To determine whether endotoxin vs. placebo will increase milliliters of alcohol consumed in women and men. Linear mixed models with intervention condition (0.4ng/kg i.v. endotoxin or placebo) and sex as between subject factors will be used to evaluate milliliters consumed during ad-libitum drinking collected in the laboratory. All interactions will be considered. The best fitting variance-covariance structure will be assessed using information criteria. The mixed effects approach is advantageous in that it is unaffected by randomly missing data and allows greater flexibility in modeling the correlation structure of repeated measures data. This data will generate effect sizes for the interaction between sex and intervention (endotoxin vs. placebo) on alcohol use.

We will evaluate the safety and tolerability of endotoxin in combination with alcohol in individuals with AUD. Participants will be assessed for altered alcohol intoxication and risks associated with endotoxin (e.g., flu-like symptoms [chills, nausea]). We will take extra safety precautions when assessing adverse effects of LPS and alcohol co-administration, including drawing serum endotoxin during alcohol self-administration and discharge.

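### The consumption model leaves out the 90-day drinking measure taken before randomisation; prespecifying it as one covariate costs one degree of freedom and gains precision if the within-sex correlation exceeds about 0.2

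*Combined protocol and SAP*

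**What the plan says.** Statistical Considerations sets out a linear mixed model in which "intervention condition (0.4ng/kg i.v. endotoxin or placebo) and sex as between subject factors will be used". The outcome is the volume drunk in the self-administration session; in the plan's words, the model is there to "evaluate milliliters consumed during ad-libitum drinking collected in the laboratory". The section adds that "All interactions will be considered". With two factors listed, that means treatment by sex. No baseline covariate is named there or elsewhere in the document.

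Eligibility Criteria describes screening, where "We will record alcohol use over the prior 90 days with the Timeline-Follow Back Interview". The same section then says that "Eligible subjects will be randomized to receive endotoxin or placebo". The 90-day record is therefore a pre-treatment measurement.

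The Inclusion Criteria add that a participant "Must meet drinking criteria during a consecutive 30-day period within the 90 days prior to baseline". Some account of drinking over that window is thus needed for everyone who enters.

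On size and design, Study Design and Methods states: "We will recruit 32 individuals with AUD (50% women"), and "Subjects will undergo a single laboratory session in which we will evaluate alcohol consumption". No power calculation, standard deviation, alpha level or precision target accompanies the 32.

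**The concern.** With one session per person, nobody serves as their own control. Whatever makes one participant a heavier drinker than another goes into the error term unless the model accounts for it. Usual drinking is an obvious candidate predictor of laboratory intake, it is measured before allocation, and using it adds no burden.

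Two things are at stake in a trial of 32. Unexplained variation between people widens the interval around each effect. And with about 16 per arm, the arms can differ by chance in usual drinking, which shifts the unadjusted estimate in that particular trial. The stated product of the analysis is effect sizes, so both matter.

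There is also a prespecification issue. Screening collects several drinking measures (the 90-day record, the Lifetime Drinking History and the AUDIT). If none is named now, any later adjustment becomes a choice among covariates made with the results in hand.

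**Working it through.** **Inputs from the document.** 32 participants, half women; two randomised groups; one session each; model terms treatment, sex and their interaction.

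**Assumptions, because the document is silent.** 1:1 allocation within sex, so 16 per arm and 8 per cell; one consumption total per person; no dropout; two-sided 5% test; outcome SD of 1 within cells, so effects are in SD units; within-sex correlation *r* between usual drinking and consumption varied from 0 to 0.7. Only the within-sex correlation counts, because sex is already in the model.

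The plan states no power or precision figure, so there is none to reproduce.

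**Step 1: unadjusted benchmark.** Residual degrees of freedom: 32 − 4 = 28.
- Standard error of the treatment effect: √(1/16 + 1/16) = 0.354 SD.
- Standard error of the interaction (difference of differences): √(4/8) = 0.707 SD.
- Detectable effect at 80% power (noncentral t, 28 df) is about 2.90 standard errors: 1.03 SD for treatment and 2.05 SD for the interaction.

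**Step 2: chance imbalance.** The arm difference in mean baseline drinking also has a standard error of 0.354 of its own SD. A difference above 0.5 SD is 0.5/0.354 = 1.41 standard errors, which happens in about 16% of trials. At *r* = 0.5 it moves the unadjusted estimate by 0.5 × 0.5 = 0.25 SD.

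**Step 3: one covariate added.** Residual df become 27. The residual variance is multiplied by (1 − *r*²). The expected price of estimating the covariate slope is a factor 1 + 1/26. The variance of the estimate, adjusted over unadjusted, is therefore (1 − *r*²) × 27/26, and the equivalent unadjusted N is 32 divided by that ratio.

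| Assumed *r* | Variance ratio | SE ratio | Equivalent N | Detectable treatment effect (SD) | Detectable interaction (SD) |
|---|---|---|---|---|---|
| unadjusted | 1 | 1 | 32 | 1.03 | 2.05 |
| 0 | 1.04 | 1.02 | 30.8 | 1.05 | 2.09 |
| 0.2 | 1.00 | 1.00 | 32.1 | 1.03 | 2.05 |
| 0.3 | 0.945 | 0.97 | 33.9 | 1.00 | 2.00 |
| 0.5 | 0.78 | 0.88 | 41.1 | 0.91 | 1.81 |
| 0.7 | 0.53 | 0.73 | 60.4 | 0.75 | 1.50 |

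**Step 4: break-even.** (1 − *r*²) × 27/26 = 1 gives *r*² = 1/27, so *r* is about 0.19.

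**Step 5: simulation check.** With 10,000 trials per scenario and 8 per cell, the variance ratios were 1.036, 1.000, 0.943, 0.771 and 0.539 for *r* = 0, 0.2, 0.3, 0.5 and 0.7, in line with the formula. For an assumed true effect of 0.8 SD, calculated power is 59% unadjusted; simulated power with adjustment was 57%, 59%, 62%, 69% and 85%. The mean 95% interval width went from 1.43 to 1.27 SD at *r* = 0.5, but rose to 1.46 SD at *r* = 0. Type I error at *r* = 0.5 was 5.1% with adjustment.

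**Step 6: a ceiling on intake.** Study Design and Methods supplies a fixed quantity aimed at a blood alcohol level of 0.12 g/dL. If half the participants finished it, a correlation of 0.5 would fall to about 0.43. The variance ratio would then be about (1 − 0.43²) × 27/26 = 0.85.

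**The case against.** The strongest reply is that the randomised comparison is unbiased without any covariate, and that the benefit of adding one depends on a correlation the documents never give. Both points stand. A reader might infer that the plan throws away precision at no cost. It does not: adjustment uses one of 28 degrees of freedom, raises the variance by about 4% if the covariate is useless, and roughly breaks even at *r* = 0.2.

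There are also reasons within the protocol why *r* might be low. The supplied quantity caps intake. The outcome is in millilitres of a beverage the participant chooses; if that means beverage volume, drink strength could dominate the variation and a count of drinks might predict it poorly.

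A reader might further infer from the entry floors (more than 14 drinks a week for men, more than 7 for women) that usual drinking is widely spread. A floor without an upper limit makes that plausible, but the documents report no spread, and the AUDIT, withdrawal and liver-enzyme exclusions indirectly limit severity. The difference between the male and female floors adds nothing, since sex is already in the model.

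What does not stand is the step from an unknown *r* to leaving the measure out. The trade is lopsided: about 2% on the standard error at worst, against a reduction of about 12% at *r* = 0.5 and 27% at *r* = 0.7.

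**Conclusion.** The point holds as one of efficiency and prespecification. The model omits a relevant pre-randomisation measure that the trial already collects, in a single-session design of 32 where differences between people go into the error term. Across the assumed range of *r* from 0 to 0.7, adjusting for it is worth between about 1 participant lost and 28 gained (equivalent N of 31 to 60), with break-even near *r* = 0.2. These figures rest on 1:1 allocation within sex, one total per person and no dropout.

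The documents do not support two stronger readings. The unadjusted analysis is not biased or invalid. And adjustment does not make the sex-by-treatment interaction well estimated: at *r* = 0.5 the detectable interaction is still about 1.8 SD, against 2.05 SD without adjustment.

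**What to change.** In Statistical Considerations, prespecify one covariate: mean drinks per day over the 90-day Timeline Follow-Back. Name that single summary, so that no choice remains between it and, for example, drinks per drinking day.

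State that it enters as a main effect only, and limit the sentence on interactions to treatment by sex. Otherwise the covariate would bring its interactions with treatment, with sex and with both, for four of the 28 residual degrees of freedom instead of one. Centring the covariate within sex is unnecessary for this purpose: with sex in the model it leaves the treatment and interaction estimates unchanged and alters only the sex term.

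Make the adjusted treatment effect and treatment-by-sex interaction primary, and report the unadjusted estimates alongside. The cost is a short addition to the plan and one degree of freedom, with no new data collection. The wording should be fixed before any outcome is examined by arm.
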